8 STATISTICAL METHODS

Endpoints will be summarized with descriptive statistics by treatment group and visit. For continuous variables, the following information will be presented: n, mean, standard deviation, median, minimum and maximum. For categorical variables counts and percentages will be used.

Baseline for all measures will be the last recorded value prior to the start of treatment.

8.1 Decision Rule and Sample Size

The comparisons related to the primary and key secondary endpoints will be done in a hierarchical manner to control the familywise error rate. The testing procedure will start by testing the primary endpoint and then proceed to the key secondary endpoints by following the order as specified in [Section 8.9.4](#).

A total of 170 subjects (85/arm) in 1:1 ratio to serlopitant 5 mg or placebo will provide 90% power to detect a 25% relative reduction (placebo-adjusted ratio of 0.75) in 24-hour objective cough frequency or awake objective cough frequency using a two-sample t-test at a one-sided significance level of 0.05. This assumes that 24-hour cough frequency or awake cough frequency follows a log-normal distribution with a CV of 0.64. This sample size also considers an expected dropout rate of 15%.

The sample size calculations have been performed in nQuery Advisor + nTerim.

8.2 Handling of Missing Data and Excluded Therapy Use

For summary statistics results will generally be reported based upon observed data. Should a determination of treatment period (on treatment, pre-treatment) be required for AEs or concomitant medication but the corresponding date is missing, or is a partial date, the event/medication will be considered on treatment unless the portions of the date that are available indicate this is not possible.

In case of missing data for the primary efficacy endpoint, two selected imputation approaches are specified for the sensitivity analyses ([Section 8.9.2.1](#)). All other efficacy endpoints, analysis will be conducted based on the observed data only.

8.3 Derivations of Efficacy Variables

The 24-hour cough frequency (coughs per hour) for a specified visit is calculated as:

24-hour cough frequency = (total number of cough events during the monitoring period (24-hour interval))/24

The awake cough frequency (coughs per hour) is defined as below:

Awake cough frequency = (total number of cough events during the monitoring period (24-hour interval) the subject is awake)/(Total duration (in hours) for the monitoring period the subject is awake)

Awake duration (hours) is time between waking up and sleep during the 24-hour monitoring period.

The cough data will contain all cough events occurring during that 24-hour monitoring period as well as the information about “sleep time” and “awake time”. Any session with duration of recording < 4 hours will be considered as missing.

In general, each 24-hour session is composed by an awake monitoring period and a sleep monitoring period. If a subject did not wake up before the end of the recording session, it will be assumed that the subject slept for the rest of the session. The session will have missing awake time, and the rest of session will be considered under the sleep monitoring period. For any session with both sleep time and awake time missing, the entire 24-hour session will be considered under the awake monitoring period, unless the session has early termination of recording.

On each collection day, the cough count, the actual cough monitoring duration (in hours), and the coughs per hour will be derived for the total 24-hour period, the awake period, and the sleep period, respectively.

The percent change in 24-hour coughs per hour is defined as below:

Percent change in 24-hour cough frequency =

$$\left[\frac{(\text{Change from baseline in 24-hour cough frequency} \times 100)}{(\text{Baseline 24-hour cough frequency})} \right]$$

The proportion of participants with $\geq 30\%$ of reduction from baseline in 24-hour cough frequency is the number of participants with $\leq -30\%$ change in 24-hour cough frequency divided by the total number of participants with available data.

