### 7.3 Analysis Windows

The analysis windows used to report cough frequency endpoints are outlined in Table . If more than one assessment is available within the range the assessment closest to the target day is reported for the analyses window. If two observations exist with the same distance to the target day, the first observation is used.

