## 8.4 Data Handling Rules for Cough Analysis

The 24-hour cough frequency (coughs per hour) for a specified visit is calculated as:

$$\text{24-hour cough frequency} = \frac{\text{total number of cough events over 24-hour monitoring period}}{\text{Total duration (in hours) over 24-hour monitoring period}}$$

The awake cough frequency (coughs per hour) is defined as below:

$$\text{Awake cough frequency} = \frac{\text{total number of cough events during the monitoring period the subjects is awake}}{\text{Total duration (in hours) for the monitoring period the subject is awake}}$$

Awake duration (hours) is time between waking up and sleep during the 24-hour monitoring period.

The cough data will contain all cough events occurring during that 24-hour monitoring period as well as the information about “sleep time” and “awake time”. Any session with duration of

recording < 4 hours will be considered as missing. Repeated monitoring may be conducted when there is an equipment failure or an unacceptable evaluation from the initial monitoring.

In general, each 24-hour session is composed by an awake monitoring period and a sleep monitoring period. If a subject did not wake up before the end of the recording session, it will be assumed that the subject slept for the rest of the session. The session will have missing awake time, and the rest of session will be considered under the sleep monitoring period. For any session with both sleep time and awake time missing, the entire 24-hour session will be considered under the awake monitoring period, unless the session has early termination of recording.

On each collection day, the cough count, the actual cough monitoring duration (in hours), and the coughs per hour will be derived for the total 24-hour period, the awake period, and the sleep period, respectively.

The percent change in 24-hour coughs per hour at each specific visit is defined as below:

percent change in 24-hour cough frequency =

$$[(\text{change from baseline in 24-hour cough frequency} \times 100) / (\text{baseline 24-hour cough frequency})]$$

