### **9.6.3.2 Cough Frequency Responder Analysis**

Two key cough frequency responder endpoints are:

- Proportion of subjects with  $\geq 30\%$  reduction in 24-hour objective cough frequency per hour at Week 12 (Day 84)
- Proportion of subjects with  $\geq 30\%$  reduction in awake objective cough frequency per hour at Week 12 (Day 84)

The proportion of participants with  $\geq 30\%$  of reduction from baseline in 24-hour cough frequency at each specific visit is the number of participants with  $\leq -30\%$  change in 24-hour cough frequency divided by the total number of participants with available data at the specific visit. Similar definition will be applied for awake cough frequency.

In addition, the exploratory analyses of  $\geq 50\%$  of reduction and  $\geq 70\%$  of reduction will be conducted for both 24-hour and awake cough frequency.

Moreover, for categorical analysis, three responder variables for 24-hour or awake objective cough frequency will be defined based on the magnitude of the percent change from baseline.

$\geq 70\%$  Reduction = 1 if Percent Change from Baseline in cough frequency at each visit  $\leq -70.0\%$ ; 0 Otherwise

$\geq 50\%$  Reduction = 1 if Percent Change from Baseline in cough frequency at each visit  $\leq -50.0\%$ ; 0 Otherwise

$\geq 30\%$  Reduction = 1 if Percent Change from Baseline in cough frequency at each visit  $\leq -30.0\%$ ; 0 Otherwise

Note that these responder definitions are not mutually exclusive. In particular, a subject who achieves a 1 for  $\geq 70\%$  Reduction, will, by definition, be classified as a 1 for  $\geq 50\%$  Reduction and  $\geq 30\%$  Reduction. The count and percentage of subjects who meet the responder criteria for  $\geq 70\%$  Reduction,  $\geq 50\%$  Reduction, and  $\geq 30\%$  Reduction will be summarized by treatment group and by visit.

For cough frequency responder endpoint, the primary analysis for the comparison of response rates between each of the serlopitant 5 mg and placebo will be conducted using the stratified Cochran Mantel Haenszel (CMH) test (stratified by country and sex, unless stated otherwise). Missing data will be categorized as discontinued or missing. Furthermore, the differences in proportions between two treatment groups will be estimated using the stratified Miettinen and Nurminen (M&N) method. A sample of SAS code for categorical analysis is provided in Appendix A.

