## APPENDIX C: STUDY VISIT MAP WITH MATCHED INTERVAL ID

## Study Visits and Matched Interval IDs in Datasets

Study Procedures	Screening	Baseline	Treatment Period						Follow-up	
	Screening	Day 0 Study Day -1	Day 1	Day 14	Day 28	Day 56	Day 84	Day 85 /ETD	Day 112	Day 113
VISITNUM	1	2	3	4	5	6	7	8	9	10
Interval ID	148	149	150	151	155	156	157	158	159	160
Study Visit Window			1 ST DAY DOSING	± 3	± 3	± 3	± 3	± 3	± 3	± 3
Vital Sign Data a	X	X	X		X	X	X	X		X
Cough Severity VAS Monitoring Data a	X	X			X	X	X	X	X	X
Telephone Contact Data a				X						
Cough Monitoring Data b		X			X	X	X		X	

a Data collected at visits marked as X. Visit dates will be derived based on the following three datasets: vital sign, cough severity VAS monitoring, and telephone contact. If there is any discrepancy in a visit date, the date recorded in vital sign dataset will be considered as the primary date.

b The cough monitoring data has regular visits labeled as Baseline, Day28, Day56, Day84, and Day112, and the repeated visits labeled as Baseline-R, Day28-R, Day56-R, Day84-R and Day112-R. Both regular and repeated records at the specific visit will be included in analysis data. Repeated evaluations are usually due to equipment failures or unacceptable initial evaluations.

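### The primary cough-frequency variable has two denominators, a fixed 24 in protocol 8.3 and recorded hours in SAP 8.4, and neither is reliable for the shortened sessions that both documents accept

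*Protocol*

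**What the plan says.** Protocol 8.3 gives the formula "24-hour cough frequency = (total number of cough events during the monitoring period (24-hour interval))/24". Further down, the same section says that on each collection day "the actual cough monitoring duration (in hours), and the coughs per hour will be derived for the total 24-hour period", and likewise for the awake and sleep periods. SAP 8.4 uses the same numerator over "Total duration (in hours) over 24-hour monitoring period". No passage says which formula prevails.

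Both documents expect incomplete recordings. They mention early termination of a session, and the only minimum is "Any session with duration of recording < 4 hours will be considered as missing" (same rule in SAP 8.4). No minimum coverage of waking or sleeping hours is set. Footnote g of the visit schedule (protocol Appendix A, SAP Appendix B) has the monitor attached before 10 am and worn for 24 hours.

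On repeats, SAP 8.4 says "Repeated monitoring may be conducted when there is an equipment failure or an unacceptable evaluation from the initial monitoring", and SAP Appendix C, footnote b, adds "Both regular and repeated records at the specific visit will be included in analysis data". Where a window holds more than one record, SAP 7.3 says "the assessment closest to the target day is reported for the analyses window", with ties going to the first. Table 2 extends Week 12 to the earlier of Day 91 and seven days after the last study medication. The text below the table assigns any assessment after the date of last study medication to follow-up.

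The responder proportion (H3 in SAP 8.7) is the number of responders "divided by the total number of participants with available data at the specific visit".

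**The concern.** The variable is the primary endpoint (H1) and the basis of the 30% responder endpoint (H3). A session of, say, 10 h counts as available data and enters both analyses as a full 24-hour value, but that value depends on which document the programmer follows. Division by 24 treats the 14 missing hours as cough-free and reads low. Division by recorded hours treats the missing hours as if they resembled the recorded ones. With a morning start the missing hours are the evening and night, so that value reads high if subjects cough less asleep.

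The planned sensitivity analyses (SAP 9.6.5) address missing values, not short sessions that count as observed. A repeat recording can repair a short session only if it is the one selected, and after baseline SAP 7.3 does not look at completeness. A Day 84 repeat meets a further problem. Dosing ends that day and protocol 6.5.8 collects the bottles at that visit, so a repeat would normally follow the last dose, where Table 2 and the text below it assign it to different visits.

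**Working it through.** **Inputs from the documents (protocol 8.1, SAP 8.2).** Ratio 0.75, CV 0.64, one-sided 0.05, 85 per arm, 15% dropout.

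**Assumptions.** The documents give no sleep hours, sleep cough rate or frequency of short sessions. I take 16 h awake, then 8 h asleep, and a sleep/awake rate ratio r = 0, 0.2 or 0.5. A session that stops by 16 h is then all awake.

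**Sample size.** Log-variance = ln(1 + 0.64²) = 0.3433 (SD 0.586); effect = −ln 0.75 = 0.2877; 85 × 0.85 ≈ 72 evaluable per arm. The noncentral t gives power 90.1%, so the planned figure reproduces.

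**Error of one all-awake session of T hours.** The true 24-hour rate, in units of the awake rate, is (16 + 8r)/24.
- Fixed 24: recorded/true = T/(16 + 8r).
- Recorded hours: recorded/true = k = 24/(16 + 8r) = 1.50, 1.364, 1.20, whatever T is.

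| Session | Fixed 24 (r = 0, 0.2, 0.5) | Recorded hours (r = 0, 0.2, 0.5) |
|---|---|---|
| 4 h | −75%, −77%, −80% | +50%, +36%, +20% |
| 8 h | −50%, −55%, −60% | +50%, +36%, +20% |
| 14 h | −12.5%, −20%, −30% | +50%, +36%, +20% |
| 16 h | 0%, −9%, −20% | +50%, +36%, +20% |

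Recorded hours do better for the shortest sessions, but worse at 14-16 h when sleep cough is low.

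**Responder endpoint (H3).**
- Fixed 24, complete baseline, unchanged subject: false responder if T ≤ 0.7 × (16 + 8r) = 11.2, 12.3, 14.0 h. At a constant rate (r = 1) the cut-off is 0.7 × 24 = 16.8 h.
- Recorded hours, short Day 84: the true reduction needed to count as 30% is 1 − 0.7/k = 53%, 49%, 42%.
- Recorded hours, short baseline that is not repeated, complete Day 84: an unchanged subject reads 1/k − 1 = −33%, −27%, −17%.

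**Power for H1 with recorded hours, truncation equal in both arms.** If a proportion p of Day 84 sessions is all-awake, the added log-variance is p(1 − p)(ln k)².
- p = 5%: 0.0078, 0.0046, 0.0016; power 89.5%, 89.8%, 90.0%.
- p = 10%: 0.0148, 0.0087, 0.0030; power 89.0%, 89.4%, 89.9%.
- Baseline affected too: take r = 0.1, p = 10% and short-session lengths spread evenly over 4-24 h. The log error has mean 0.280 and root mean square 0.302. The variance per visit is 0.1 × 0.302² − 0.1² × 0.280² ≈ 0.0083. Twice that, added to 0.3433, gives power of about 88.8%.

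**H3 difference.** With log-normal change and an assumed placebo ratio of 1.0, the responder rates are 27.1% and 45.3%, a difference of 18.2 points. With 10% short Day 84 sessions in both arms it is 17.5, 17.7, 17.9 points.

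**Imbalance.** Five points more short Day 84 sessions in one arm multiply a true ratio of 1.00 by exp(0.05 ln k) = 1.020, 1.016, 1.009.

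**The case against.** The strongest reply is that protocol 8.3 qualifies its formula with a 24-hour interval and then says that actual duration will be derived. With SAP 8.4 the intention is fairly clear, and only a line of protocol wording is needed. With recorded hours the loss is about one percentage point of power at an assumed 10% of short sessions. Awake cough frequency (H2) is divided by awake hours, so losing the night does not inflate it. Repeats also cover unacceptable evaluations, not only sessions under 4 h.

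Much of this stands. A reader might infer that the fixed 24 will be applied and will distort the primary result. The documents do not support that: the SAP and the protocol's own later sentence point to recorded hours. A reader might also infer that a short baseline stays in use even when repeated. It does not: Table 2 targets Day 1 for baseline, so a later pre-dose repeat is closer and is selected, and protocol section 8 takes the last value before treatment. The short-baseline error therefore applies only where the baseline is not repeated.

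The reply does not dispose of three things. The printed protocol formula still contradicts the SAP on the primary variable. A sound H2 does not correct H1 or H3. Repeats are optional, and after baseline nothing favours the complete record.

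**Conclusion.** The concern holds, as something that should be fixed before unblinding. The contradiction between the formulas, the acceptance of any session of 4 h or more, and the conflict within SAP 7.3 are plain in the text.

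Its size rests on assumed sleep hours, sleep cough rates and frequencies of short sessions. For a single subject the error can be large under either formula and runs in opposite directions. It would be wrong to conclude that adopting the SAP formula always leaves the smaller error, or that it closes the matter.

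For the trial as a whole, with recorded hours and balanced truncation, the effect is small: added noise, some misclassified responders, and power of about 89-90%, or about 88.8% if baselines are affected too. A reader might infer a biased treatment effect. That needs short sessions to be more frequent in one arm, and the documents give no reason to expect it.

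**What to change.** 1. In protocol 8.3, make recorded hours the single denominator, matching SAP 8.4.
2. In SAP 7.3, reconcile Table 2's limit of seven days after the last study medication with the sentence assigning every later assessment to follow-up.
3. In SAP 7.3, when a first and a repeat record fall in the same reconciled window, use the more complete one. Do not add a separate on-treatment condition, which would normally exclude a Day 84 repeat.
4. Keep the 4 h rule in the primary analysis. In SAP 9.6.5, prespecify one sensitivity analysis of H1 and H3 that excludes sessions not covering the sleep period and most of the 24 h. The sponsor should fix and justify the cut-off before unblinding. At 22 h, for example, with all 8 h of sleep captured and r = 0, the residual error is (14/22)/(16/24) − 1 = −4.5%. Report short sessions by arm and visit.

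The cost is wording plus one analysis. The full analysis set, the primary analysis and its power are unchanged. Subjects with a short, unrepeated baseline drop out of the sensitivity analysis only. If 5-10% of Day 84 values are excluded there, 72 per arm becomes 68 to 64 and power about 88.6% to 86.8% by the t-test approximation; the repeated-measures model recovers part of that from Days 28 and 56.

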8.4 Analysis Populations

The FAS will serve as the primary population for the analysis of efficacy data in this study. The FAS consists of all randomized subjects who have taken at least one dose of study medication and provided at least one baseline and at least one post-baseline primary endpoint observation during the treatment period. Subjects will be analyzed according to the treatment group to which they are randomized.

The safety analysis set will be used for the analysis of safety data in this study. The safety analysis set will consist of all subjects randomized who receive at least one dose of study medication. Subjects will be classified based upon the treatment received. For safety analyses, subjects will be classified based upon the treatment received.

The PK analysis set will consist of all subjects who receive ≥ 1 dose of serlopitant and who have at least 1 post-dose PK blood sample available for analysis.

8.5 Subject Disposition

An accounting of all randomized subjects by disposition will be presented. Subjects who discontinue study drug prematurely or withdraw from the study will be summarized and listed, with a description of the reason for early termination/withdrawal.

8.6 Subject Characteristics

Demographic and other baseline characteristics will be summarized. Duration of chronic cough (years) will be derived as year of informed consent minus year of start date of the chronic cough medical history.

8.7 Concomitant Medications

Concomitant medications will be coded by the World Health Organization (WHO) Drug Dictionary to Anatomical Therapeutic Classification (ATC) and preferred drug name. Concomitant medications will be summarized by ATC level and preferred drug name and listed.

8.8 Treatment Compliance and Extent of Exposure

Percent compliance will be calculated for each subject as below:

$$\text{Percent Compliance} = \frac{\text{Number of Days on Therapy}}{\text{Number of Days Should Be on Therapy}} \times 100\%$$

A day within the study will be considered an “On-Therapy” day if the participant takes all required medication. If a subject misses a daily dose, that day is not considered an On-Therapy day.

The duration of exposure for each participant will be evaluated by calculating the number of days on therapy.

Percent compliance and duration of exposure to study medication will be summarized using descriptive statistics (mean, SD, median, minimum, and maximum) for the safety analysis set.

8.9 Efficacy Analyses

8.9.1 *Statistical Hypotheses and Tests*

The study is designed to evaluate, the efficacy of serlopitant 5 mg relative to placebo. The primary hypothesis for this trial is that serlopitant is superior to placebo with respect to the mean change from baseline in 24-hour cough frequency (on the log scale).

Symbolically, the hypotheses for serlopitant 5 mg compared to placebo can be written as:

$$H_0: \mu_{SP, \text{Week 12}} - \mu_{SP, \text{Baseline}} = \mu_{PL, \text{Week 12}} - \mu_{PL, \text{Baseline}}$$

$$H_A: \mu_{SP, \text{Week 12}} - \mu_{SP, \text{Baseline}} < \mu_{PL, \text{Week 12}} - \mu_{PL, \text{Baseline}}$$

where μ_{SP} and μ_{PL} represent the mean values at Week 12 for serlopitant 5 mg and placebo, respectively.

As the primary endpoint, cough frequency, is to be analyzed on the log scale the null hypothesis relates to the ratio of Week 12/Baseline for serlopitant 5 mg being the same as that for placebo, and the alternative hypothesis being that the ratio of Week 12/Baseline for serlopitant 5 mg is smaller than the ratio for placebo.

A family wise error rate will be controlled to adjust for multiplicity for the comparison of serlopitant 5 mg to placebo on the primary and key efficacy endpoints in a hierarchical manner (see details in [Section 8.9.4](#)).

8.9.2 *Primary Endpoint*

The primary efficacy endpoint of this study is change from baseline in 24-hour objective cough frequency at each dose studied after 12 weeks of treatment. A negative result indicates a decrease in cough frequency, while a positive result indicates an increase in cough frequency.

As the change in 24-hour cough frequency may have a skewed and wide distribution, the primary analysis for the primary endpoint will be on the natural log scale of the cough frequency data. The difference between serlopitant 5 mg and placebo will be estimated using a mixed effect repeated measures (MMRM) model. The model will include factors for treatment, visit, country, sex, the treatment-by-visit interaction; and the log-transformed baseline value as a covariate. The MMRM model will use all available 24-hour cough frequency data on Day 28, 56, and 84. An unstructured covariance structure will be applied for MMRM. In case the model will not converge with the unstructured covariance structure, the heterogeneous compound symmetry (CSH) will be used instead. Contrasts will be constructed to compare the serlopitant 5 mg group to the placebo group at each visit. The least-squares (LS) mean change from baseline (on the log scale) with the associated standard errors will be displayed for each treatment group. Estimated treatment differences (serlopitant vs. placebo) along with corresponding CIs will also be presented.

In addition, the geometric mean of 24-hour cough frequency will be presented by treatment and by visit. The percent difference change between serlopitant and placebo will be estimated

by $100(e^{\text{diff}} - 1)$, where diff is the difference provided by the analysis of the log-transformed variable.

An observation of zero coughs per hour will be replaced by a cough rate of 0.1/hr for the calculation of geometric means. If this rule is used the table will have a footnote detailing the participant and treatment. Further details of the model specification, assumptions, and SAS implementation codes will be provided in the SAP.

Furthermore, the changes from baseline in 24-hour cough frequency on the original scale will be also analyzed using a the same MMRM model.

